## CONFIDENTIEL / CONFIDENTIAL

## STATISTICAL ANALYSIS PLAN

### 2.1.4. Data Listings

Patient data listings will be selected data supportive of summary statistical tables, including derived/calculated data from statistical process. These key data listings will be performed on selected analysis sets according to the focus of the listings.

### 2.3. Analysis Sets

#### 2.3.1. Definition of patient populations

2 populations will be defined:

- The “included” population will include all patients enrolled in the study.
- The Per Protocol (PP) population will include all “included” patients for whom the GORE® TAG® and Conformable GORE® TAG® thoracic endoprosthesis were introduced through surgical or percutaneous approach, and who fulfill the eligibility criteria.

### 2.4. Statistical Analyses

All analyses will be conducted on the PP population.

The “included” populations defined in section 2.3.1 will only be used to list the patients who do not fulfill the eligibility criteria.

#### 2.4.1. Patient Disposition

The following items will be presented:

- The number of included and PP patients (globally and by center) as well as a listing of non-included patients and patients excluded from the PP population
- A study flowchart table will be presented on the PP population and the reasons of interruption will be specified.
- Study duration:
  - The total study duration (between procedure and study exit) will be presented globally.
  - The study follow-up duration (between procedure and the last available follow-up) will also be presented in intermediary report(s).

## STATISTICAL ANALYSIS PLAN

### 2.4.2. Patient Characteristics

Descriptive statistical data will be used to draw up a recapitulation of PP patients at baseline, procedure and follow-up.

#### 2.4.2.1. Baseline

- Demographics
- Medical condition (Medical history / risks factors, patient symptoms)
- Patient participation in another W.L. Gore study
- Life-threatening emergency
- Main indication for implantation
- Dissections and trauma patients characteristics
- Procedure planning

#### 2.4.2.2. Procedure

- Implantation parameters
- Procedure evaluation and results
- Device used
- Imaging abnormalities
- Time spent in ICU

#### 2.4.2.3. Follow-up

The following items will be presented at each visit:

- Measurements and dissections characteristics
- Imaging abnormalities

### 2.4.3. Endpoints Analyses

#### 2.4.3.1. Primary Analysis

The primary endpoint is the all-cause mortality rate over the long term, which is 5 years.

The 5-year mortality is defined for all deaths occurring between the time of surgery when the endoprosthesis was inserted into the arterial access and the last follow-up visit at 5 years.

It will be presented as a categorical variable (with the corresponding 95% bilateral CI), overall and by visit, and described over time by a survival curve as per the Kaplan-Meier method together with the associated estimators.

The primary endpoint will also be analyzed depending on the life-threatening emergency and by main indication for implant (aneurysm, dissection, ulcer and trauma).

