## 2. STATISTICAL METHODS

### 2.1. General Statistical Considerations

#### 2.1.1. Descriptive Statistics in Summary Tables

- Continuous variables will be summarized using standard quantitative statistics: number of non-missing observations, mean, standard deviation, median, quartiles and range (minimum and maximum observed values). The number of missing observations will also be specified.
- Categorical variables will be summarized using classical frequency statistics: number of non-missing observations and percentages by categories. Percentages will be calculated on the number of non-missing observations and will be displayed using one decimal, the corresponding bilateral 95% CI will be presented if appropriate. The number of missing observations will also be specified.

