#### 2.1.3. Handling Missing Data

No replacement of missing data is planned.

If a patient interrupts the study before the end of study, he/she will be considered as missing from his/her last follow-up.

Patients will be considered as censored at the date of the last observation in survival analyses.

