## Endpoints Analyses

### Primary Analysis

Table 46: Mortality – by time point (Type 4)

Table 47: Mortality by life-threatening emergency – by time point (Type 4)

Table 48: Mortality by main indication for implantation – by time point (Type 4)

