## 4.2. Graphs

Graph 1: Mortality survival analysis (Type 9)

Graph 2: Mortality by life-threatening emergency - survival analysis (Type 9)

Graph 3: Mortality by main indication for implantation survival analysis (Type 9)

Graph 4: Neurological complications survival analysis (Type 9)

Graph 5: Cardiac, renal and pulmonary complications survival analysis (Type 9)

Graph 6: Device-related complications survival analysis (Type 9)

Graph 7: Surgical conversion survival analysis (Type 9)

Graph 8: Secondary procedures survival analysis (Type 9)

Graph 9: Mortality related to the disease survival analysis (Type 9)

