## STATISTICAL ANALYSIS PLAN

### 5.3.2. Survival curve (Type 9)

#### Summary table

	Mod 1 (n=X)	...*	Mod n* (n=X)	Log-Rank test
Nb of patients	X	...	X	
Nb of patients with an event	XX (XX.X%)	...	XX (XX.X%)	0.xxx
Nb of patients without an event	XX (XX.X%)	...	XX (XX.X%)	
Survival rate	XX%	...	XX%	
Progression-Free survival (days)		...		
Median	XX	...	XX	
(95% CI)	(XX.X, XX.X)	...	(XX.X, XX.X)	
25th-75th percentile	XX.X – XX.X	...	XX.X – XX.X	
Range	XX.X – XX.X	...	XX.X – XX.X	

\* If any

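### The only 95% CI specified for 5-year mortality is on a crude percentage that incomplete vital status can bias; the planned Kaplan-Meier analysis has no stated 5-year estimate or CI

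*SAP*

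**What the plan says.** SAP 2.4.3.1 describes two presentations of 5-year all-cause mortality. The first is a proportion: "It will be presented as a categorical variable (with the corresponding 95% bilateral CI), overall and by visit". The second is a curve: mortality is "described over time by a survival curve as per the Kaplan-Meier method together with the associated estimators". Both are repeated by life-threatening emergency and by main indication (Tables 46-48, Graphs 1-3). The SAP does not say which is the primary estimate.

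Four places bear on the denominator of the proportion:

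- SAP 2.1.1: "Percentages will be calculated on the number of non-missing observations".
- SAP 2.1.3: nothing is replaced, and of a patient who stops early, "he/she will be considered as missing from his/her last follow-up".
- SAP 5.2.2: the Type 4 shell used for Tables 46-48 has a separate row for missing values.
- SAP 2.5: an adverse event, or any other item not reported on a follow-up form, counts at 5 years if it falls between the procedure and day 1826. No missing category is given. The flowchart in SAP 1.3.4 places death on the adverse event and study exit forms, not the follow-up form.

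For the curve, SAP 2.1.3 says: "Patients will be considered as censored at the date of the last observation in survival analyses". The Type 9 shell (SAP 5.3.2) has a row "Survival rate" with no time point and no CI. Its only CI belongs to the median.

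Protocol 5.4.2 requires alive/dead status to be confirmed through the national cause-of-death centre and entered in the eCRF when other contact fails. The SAP does not mention this tracing.

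Protocol 9.1 and 9.4, SAP 2.2 and parts of SAP 1.3 are not shown, so what follows concerns the visible text only.

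**The concern.** The study has one arm and no comparator, so its primary result is a mortality estimate and an interval. The data are required for renewal of registration (protocol 1.2.2). The figure that carries the specified interval is the one that depends on complete follow-up. The planned method that handles censoring has no specified interval at 5 years. The median CI in the Type 9 shell does not fill the gap: it is not a CI for 5-year mortality, and the median would usually not be reached if 5-year mortality is well below 50%.

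A crude percentage treats early deaths and early losses unequally. A death seen before a patient would have been lost stays in the numerator. A patient lost alive either leaves the denominator, which pushes the rate up, or stays in it as if alive, which pushes the rate down. The visible text does not settle which applies, or how traced status enters.

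**Working it through.** **Inputs.** From the documents: 160 patients, 5 years, two-sided 95%. Neither expected mortality nor a loss rate is visible, and no derivation of 160 is shown, so there is no planned figure to reproduce. Assumed: all 160 are in the per-protocol set; true 5-year mortality p is 25%, 35% or 45%; vital status is unknown for u = 8%, 16% or 25%; loss is independent of death.

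**Direction.** Let F be the death distribution with density f, S = 1 - F, and G(t) the probability of not being lost by t. Known deaths have expectation D = ∫f(t)G(t)dt over 0-5 years. Known survivors have expectation C = S(5)G(5). Because G falls over time, D ≥ F(5)G(5), so D/(D+C) ≥ F(5). Because G ≤ 1, D ≤ F(5). The non-missing rate is therefore never too low, and the rate over all per-protocol patients is never too high.

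**Size.** With constant hazards, the death hazard is a = -ln(1-p)/5. The loss hazard g solves g/(a+g)·(1-exp(-5(a+g))) = u. Then D = a/(a+g)·(1-exp(-5(a+g))) and C = exp(-5(a+g)). For p = 35%, a = 0.0862. Coverage is that of the exact (Clopper-Pearson) 95% CI, with n ~ Bin(160, D+C) and x given n ~ Bin(n, D/(D+C)); for the all-patient denominator, x ~ Bin(160, D).

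| Unknown | D | C | D/(D+C) | Coverage | D over all | Coverage |
|---|---|---|---|---|---|---|
| 8% | 0.3338 | 0.5862 | 36.3% | 94.8% | 33.4% | 94.7% |
| 16% | 0.3170 | 0.5230 | 37.7% | 91.1% | 31.7% | 89.0% |
| 25% | 0.2974 | 0.4526 | 39.7% | 83.7% | 29.7% | 75.8% |

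Example at 16%: 0.3170/(0.3170+0.5230) = 37.7%.

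**Other mortality levels, non-missing denominator.** True 25%: 26.0 / 27.1 / 28.5%, coverage 95.2 / 92.8 / 87.6%. True 45%: 46.5 / 48.3 / 50.6%, coverage 94.4 / 90.1 / 79.8%. For true mortality 25 / 35 / 45%, the bias reaches 1 point at 8.3 / 6.3 / 5.3% unknown and 2 points at 15.5 / 12.1 / 10.2%.

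**Early deaths.** If 8 of the 35 points die perioperatively, the non-missing rate is 36.6 / 38.4 / 40.9%, with coverage 94.2 / 88.3 / 75.9%.

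**Kaplan-Meier at day 1826.** In 20,000 simulated cohorts of 160 per scenario, with Greenwood variance and a log-log CI, coverage was 94.7-95.2% under constant hazard. For p = 35% the half-width was 7.6 / 7.8 / 8.1 points, against 8.0 / 8.5 / 9.0 for the crude non-missing CI.

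**Tracing.** If a fraction q of those unknown is traced and both outcomes are used, D becomes D+q(p-D) and C becomes C+q(1-p-C). At 16% and q = 0.9: D = 0.3170+0.9×0.0330 = 0.3467, C = 0.5230+0.9×0.1270 = 0.6373, and the rate is 0.3467/0.9840 = 35.2%. Across 8 / 16 / 25%, 90% tracing gives 35.1 / 35.2 / 35.4% with coverage about 96%. Half tracing gives 35.6 / 36.3 / 37.0%, coverage 95.6 / 94.8 / 93.4%.

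**Informative loss.** Take 30% mortality under observation and a 20% five-year loss probability (16.9% of patients end with unknown status). If the death hazard triples after loss, the truth is 34.1%, the non-missing rate 32.6% and Kaplan-Meier 30.0%.

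**The case against.** Much is already in place. Kaplan-Meier is planned overall and by both subgroupings, and its unlisted estimators could include a pointwise 5-year CI. Type 9 is a generic layout shared by nine graphs, so its silence proves little. Tracing is mandatory, and a status entered in the eCRF is naturally a non-missing value and can serve as a last observation. No visible mortality threshold exists that a shift of one or two points could cross. These points stand, and they limit the practical weight of the issue. They do not supply a stated 5-year interval, a named primary estimate or a tracing rule.

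A reader might infer that the reported mortality is bound to be too high. The documents do not support that. SAP 2.1.1, SAP 2.1.3 and the missing row favour the non-missing denominator, but Type 4 is also a generic shell. SAP 2.5 read with the flowchart allows deaths by day 1826 over all per-protocol patients, the type of denominator the adverse event shell uses, and that rate is too low. Strongly informative loss can also reverse the direction.

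A reader might further infer that traced deaths would be counted while traced survivors stay missing. No text directs this.

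**Conclusion.** The point holds as a conditional one. In the visible text, the only interval specified for the primary endpoint is on a crude percentage. Under independent loss that percentage is biased on either reading of its denominator, upward or downward, and the text does not settle which. For a true 35%, the shift is +1.3 or -1.6 points at 8% unknown status, and +4.7 or -5.3 points at 25%. It is trivial if tracing is nearly complete: 0.1-0.4 points with 90% traced and the non-missing denominator. It matters from about 12-16% residual unknown status, where the non-missing rate is 2 points or more too high for a true 35% and coverage falls towards 91%. The mortality and loss levels are assumptions.

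Kaplan-Meier keeps nominal coverage if loss is independent of death. It is not a remedy for strongly informative loss, where it can be further from the truth than the crude rate. That is a reason to use confirmed vital status and to report how many patients remain unknown.

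**What to change.** - In SAP 2.4.3.1, name 1 minus Kaplan-Meier survival at day 1826, with a pointwise 95% CI of stated type (log-log, for example), as the primary estimate, overall and by emergency and indication group. Day 1826 is already the 5-year limit in SAP 2.5.
- In the Type 9 shell, add time points (30 days, 1 to 5 years) and 95% CIs to the survival row.
- Keep the crude counts in Tables 46-48 as descriptive, with the denominator stated.
- In SAP 2.1.3, state that confirmed vital status, dead or alive alike, sets the death or censoring date (up to day 1826) and overrides missing status for mortality.
- Report the number of patients with unknown vital status at 5 years.

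The cost is SAP wording and one table shell. No data are needed beyond the confirmation that protocol 5.4.2 already requires, with its date.

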#### 2.4.3.2. Secondary Analyses

The secondary endpoints for assessing the usefulness of the technique will be:

- The exclusion rate of the aneurysm, the false lumen, the penetrating aortic ulcer or rupture site, with no type I or III endoleak (overall and by main indication for implantation)

It will be presented as categorical variables (with the corresponding 95% bilateral CI) by time-point, starting at 30 days.

- The rate of neurological complications
- The rate of cardiac, renal and pulmonary complications
- The rate of device-related complications
- The rate of surgical conversion
- The rate of secondary procedures (re-interventions)
- The rate of mortality related to the disease

#### CONFIDENTIEL / CONFIDENTIAL

## STATISTICAL ANALYSIS PLAN

They will be presented as categorical variables (with the corresponding 95% bilateral CI) by time-point and described over time by a survival curve as per the Kaplan-Meier method together with the associated estimators.

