### 1.2. Study Design

This study is an observational, prospective, multicenter, non-randomized, single-arm and open-label which 160 patients will be enrolled from approximately 30 investigational French sites.

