## CONFIDENTIEL / CONFIDENTIAL

## STATISTICAL ANALYSIS PLAN

- Derived criterion "exclusion of the false lumen without endoleak" will be defined as follows:  
"Exclusion of the main entry of the dissection" will be YES if:
  - no false lumen perfusion type Ia, Ib, III is ticked
  - and "Incorrect Deployment" is not ticked or "false lumen perfusion through a tear proximal to the device in an untreated segment (not an endoleak)" is not ticked
  - and "Status of false lumen located opposite the treated part of the aorta" is "Complete thrombosis"
 If the perfusion status is unknown or if the false lumen thrombosis status is unknown then "exclusion of the false lumen without endoleak" will be missing.
- Derived criterion "exclusion of the penetrating aortic ulcer without endoleak" will be defined as follows:  
No maximum aortic diameter of the ulcer increase > 5 mm (compared to 1st post-op exam) and no type I or type III endoleak
- Derived criterion "exclusion of the rupture site without endoleak" will be defined as follows:  
No type I or type III endoleak
- Mortality from thoracic disease is defined as any death occurring as a result of complication of aortic disease (rupture, conversion, etc.) or following any surgery intended to treat the aortic disease. It will be derived as follows:
  - If the death occurs within 30 days after the initial procedure or any re-intervention or
  - If the death is related to the disease
 Then mortality from thoracic disease will be "YES"
- An adverse event (or any other parameter that is not reported in a follow-up CRF) will be considered as having occurred
  - "at 1 month" if it occurs between the procedure (included) and 30 days after the procedure
  - "at 1 year" if it occurs between the procedure (included) and 365 days after the procedure
  - "at 2 year" if it occurs between the procedure (included) and 731 days after the procedure
  - "at 3 year" if it occurs between the procedure (included) and 1096 days after the procedure
  - "at 4 year" if it occurs between the procedure (included) and 1461 days after the procedure
  - "at 5 year" if it occurs between the procedure (included) and 1826 days after the procedure

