### 5.3.1. Adverse events (Type 8)

Adverse events	Population (N=XX)		
	NAE (1)	n (2)	% (3)
ALL	XX	XX	XX.X
Type 1	XX	XX	XX.X
Type 2	XX	XX	XX.X
...	...	...	...
Type n	XX	XX	XX.X

[figure not shown]
(1): Number of adverse events/medication of a given type of adverse event/medication

(2): Number of patients with at least one adverse event of a given type of adverse event

(3): (n / N)\*100 (N: total number of patients)

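### SAP rules for Tables 54-59 do not fit together: they leave open whether patients who died, and events before death, stay in the 5-year rates

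*SAP*

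**What the plan says.** Tables 54-59 cover neurological complications, cardiac/renal/pulmonary complications, device-related complications, surgical conversion, secondary procedures and disease-related mortality. SAP 2.4.3.2 says: "They will be presented as categorical variables (with the corresponding 95% bilateral CI) by time-point and described over time by a survival curve". SAP 4.1 assigns all six to the Type 4 layout, which has an N, a count with percentage and CI, and a Missing row for each column.

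Three other rules bear on what is counted:

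- SAP 2.1.1 (denominator): "Percentages will be calculated on the number of non-missing observations".
- SAP 2.1.3 (missing data): "If a patient interrupts the study before the end of study, he/she will be considered as missing from his/her last follow-up". The sentence on censoring that follows is limited to survival analyses. This one is not.
- SAP 2.5 (time windows): "An adverse event (or any other parameter that is not reported in a follow-up CRF) will be considered as having occurred" at 5 years "if it occurs between the procedure (included) and 1826 days after the procedure". Every window starts at the procedure, so the status is cumulative.

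The SAP does not define an interruption. In 2.4.1 it says that "the reasons of interruption will be specified", and Table 2 reports these as study exit reasons. The SAP 1.3.4 flowchart records death on the study exit form. Protocol 5.2 lists death with loss to follow-up and withdrawal of consent as a premature end of the follow-up visits, and Protocol 5.4.1 lists it among the reasons that data collection stops.

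By contrast, the Type 8 layout used for adverse events (Table 66) divides by a fixed denominator, "N: total number of patients".

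**The concern.** Take a patient who has a stroke in the first month and dies in year 2. Under SAP 2.5 this patient is YES at 5 years. Under 2.1.3, if death is an interruption, the patient is missing at 5 years. Nothing says which rule prevails. A patient who dies in year 2 without a complication is not an event under 2.5 and is missing under 2.1.3, so leaves the denominator under 2.1.1, although it is known that no complication occurred before death.

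Two results follow on that reading. If events are kept and event-free deaths are dropped, the rate can only be too high as a proportion of treated patients. If both are dropped, the table describes 5-year survivors: complications in patients who later died disappear, and a rate defined as cumulative can fall from one visit to the next. Neither is the proportion of treated patients who had the complication.

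These tables carry most of the secondary endpoints of a study that reports each year to the health authority. Changing the method for the curves would not change them.

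**Working it through.** **Inputs.** The only figure from the documents is the cohort size: SAP 1.2 describes a study in "which 160 patients will be enrolled from approximately 30 investigational French sites". It is used here as the per-protocol number. No expected mortality, complication or loss rate is visible, so those are assumed. There is no stated 5-year rate to reproduce.

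**Formulas.** Let N = 160, E = 16 patients with an event by 5 years, D = deaths by 5 years, d = deaths among the E, and no losses.

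- All patients: E/N = 16/160 = 10.0%.
- Reading A (events kept under 2.5, event-free deaths missing): E/(N − (D − d)).
- Reading B (2.1.3 applied to everyone who died): (E − d)/(N − D).

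| D | d | Reading A | Reading B |
|---|---|---|---|
| 40 | 6 | 16/126 = 12.7% | 10/120 = 8.3% |
| 40 | 10 | 16/130 = 12.3% | 6/120 = 5.0% |
| 56 | 6 | 16/110 = 14.5% | 10/104 = 9.6% |
| 56 | 10 | 16/114 = 14.0% | 6/104 = 5.8% |
| 72 | 6 | 16/94 = 17.0% | 10/88 = 11.4% |
| 72 | 10 | 16/98 = 16.3% | 6/88 = 6.8% |

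Across the grid, reading A gives 12.3-17.0% and reading B 5.0-11.4%. Reading A always exceeds 10.0%. Reading B falls below it when event patients die more often than the cohort (10/16 = 62.5% against 56/160 = 35%) and above it when they die less often (6/16 = 37.5% against 72/160 = 45%).

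**Low mortality.** With D = 16 (10%) and d = 3: A = 16/147 = 10.9%, B = 13/144 = 9.0%, a gap of 1.9 points.

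**Adding losses.** Assume 32 patients with an event, 64 deaths (19 after an event, 45 event-free) and 16 other exits (2 after an event, 14 event-free):

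- All patients: 32/160 = 20.0%.
- Reading A, with event-free exits also missing: 32/(160 − 45 − 14) = 32/101 = 31.7% (exact 95% CI 22.8-41.7).
- Reading B: (32 − 19 − 2)/(160 − 64 − 16) = 11/80 = 13.8% (7.1-23.3).
- Event-free deaths kept as NO, only event-free living exits missing: 32/(160 − 14) = 32/146 = 21.9%.

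With the same 32 events and 5% exits, A and B are 32/125 = 25.6% and 19/112 = 17.0% at 25% deaths, and 32/142 = 22.5% and 26/136 = 19.1% at 10% deaths.

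**Simulation.** A run of 400,000 patients assumed 20% events, 40% deaths and 10% exits by 5 years, with the death hazard doubled after an event. It gave 28.0% for A, 15.3% for B, 17.9% with event-free deaths kept as NO, 20.0% for one minus Kaplan-Meier with deaths censored, and 17.2% for the Aalen-Johansen cumulative incidence. Keeping event-free deaths as NO brings the crude rate close to the cumulative incidence. The remaining 0.7 points come from dropping event-free patients who left alive.

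**The case against.** The strongest reply is that the SAP nowhere says that death is an interruption. Being on the Protocol 5.4.1 list does not make a patient missing, because the normal end of the study is on that list too. Read literally for deaths, 2.1.3 would also make the deaths themselves missing in Table 46 (the primary endpoint) and Table 59, which cannot be intended. The rules can also be reconciled: 2.5 is specific and says the event has occurred, while 2.1.3 looks forward from the last visit and suits the by-visit imaging and exclusion tables. A programmer might then divide by all per-protocol patients, as Type 8 does, and obtain the 10.0% reference value.

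Much of this stands. A reader might infer that the SAP prescribes a denominator without the deaths. It does not; that is an inference from how the documents use study exit. A reader might also infer that Table 56 must disagree with the device-related line of Table 66. It may, but only if Table 56 does not also use all patients and depending on how its endpoint is derived.

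It does not remove the point. The reconciliation is not written down, and the absurd result for Tables 46 and 59 shows that 2.1.3 needs an exception. The all-patient reading needs its own rule, since it counts patients lost alive as event-free, and the Missing row suggests that a varying denominator was foreseen.

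Two further replies are that these are descriptive tables in a single-arm study, and that Kaplan-Meier estimates are planned for the same endpoints. Both are true and limit the severity. But neither output is named as the reported rate, the curves censor deaths, and the Type 9 layout shows a CI for the median but none for the survival rate. The N and Missing rows would show a shrinking denominator but would not separate deaths from losses.

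**Conclusion.** The concern holds as an unresolved conflict between rules. SAP 2.1.3 and 2.5 give different 5-year statuses to a patient who had an event and then left the study, no precedence is stated, and the place of event-free deaths in the denominator is not settled. On the natural reading, the crude rates are either biased upward or describe survivors only.

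The size is conditional. With 160 patients, 16 events, no losses, 25-45% mortality and 6-10 deaths among event patients, the readings span 12.3-17.0% and 5.0-11.4% around an all-patient 10.0%. At about 10% mortality the two readings are about 2-3 points apart. A reader might infer that the published rates are bound to differ widely. The documents give no mortality or attrition figures to support that. The ambiguity itself does not depend on those assumptions, and it should be closed before the tables are programmed.

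**What to change.** Add to SAP 2.4.3.2 and 2.5:

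- For Tables 54-58, a patient with the event by the time point is YES whatever happens later. A patient who died event-free before the time point stays in the denominator as NO. Only patients alive and not followed to the time point are missing, and their number is shown.
- SAP 2.1.3 does not remove past events.
- For Table 59, deaths from other causes stay in the denominator as NO.
- Beside each crude rate, report an Aalen-Johansen cumulative incidence with 95% CI at each time point, with death as the competing event (for Table 59, death from other causes).

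Event-free patients lost alive are still dropped, so some upward bias remains (21.9% against 20.0% in the example with losses). A footnote should say so, and should say that the rate is the proportion affected before death. The cost is a few lines of SAP text and slightly more programming; no new data are needed.

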5.4 End of patient participation

5.4.1 Procedure to withdraw from the study

The withdrawal procedure from the study applies when patient data are no longer collected. Discontinuation of patient data collection will occur in the following cases:

- The patient decides to withdraw from the study at any time, for whatever reason, without having to justify such a decision
- Decision made by the doctor to stop the patient's participation in the study in order to protect the patient's well-being
- Patient lost to follow-up
 - Note: the patient may not be considered as being lost to follow-up by the investigator as long as the follow-up period (5 years) has not elapsed.
- Patient's death
- Normal end of the observational study

Data on patients, for whom the study endoprosthesis was introduced at the arterial access but not inserted during the initial intervention (failed installation), will be collected until the patient's withdrawal. Thereafter, a withdrawal form from the observational study must be completed.

Patients for whom the endoprosthesis will be explanted during the follow-up period should be evaluated clinically at least until the last 5-year visit.

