9 DATA ANALYSIS AND REPORTS

[figure not shown]
9.2 *Statistical criteria for discontinuing the research*

No discontinuation criterion.

9.3 *How to manage missing, unused or invalid data*

Missing data will be listed and presented in a tabulated form.

Patients will be considered as censored at the date of the last observation.

9.5 *Right of access to data and source documents*

Individuals with direct access to data in accordance with existing legislative and regulatory provisions, notably articles L.1121-3 and R.5121-13 of the Public Health Code (for example, investigators, individuals responsible for quality control, and any individuals appointed to collaborate in trials) shall take all necessary precautions to ensure the confidentiality of information relating to experimental drugs, trials, subjects involved in trials, particularly as regards their identity, and results obtained therefrom. Data collected by these people is then anonymized.

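### Six secondary endpoints are described by Kaplan-Meier with no rule for event-free death; if those deaths are censored, the 5-year complication rates are overstated

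*SAP*

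**What the plan says.** SAP 2.4.3.2 gives the exclusion rate its own sentence, as a categorical variable only. The other six secondary endpoints are to be presented as categorical variables with 95% confidence intervals "by time-point and described over time by a survival curve as per the Kaplan-Meier method together with the associated estimators". They appear as Tables 54-59 and Graphs 4-9.

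SAP 2.1.3 sets one rule for all the curves: "Patients will be considered as censored at the date of the last observation in survival analyses". Protocol 9.3 has the same rule: "Patients will be considered as censored at the date of the last observation". Protocol 5.4.1 includes the patient's death in the list introduced by "Discontinuation of patient data collection will occur in the following cases".

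For the categorical rates, SAP 2.5 uses cumulative windows, so an event belongs to the 5-year rate "if it occurs between the procedure (included) and 1826 days after the procedure". SAP 2.1.1 divides by non-missing observations.

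The survival layout (SAP 5.3.2, Type 9) prints the number and crude percentage with an event, a survival rate, and a row for progression-free survival in days. No visible text names death as a competing event, defines a composite with death, or specifies a cumulative incidence estimator. Protocol 9.1 and parts of the SAP are not shown, so nothing is claimed about what they contain.

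**The concern.** A patient who has died can no longer have a stroke, a conversion or a re-intervention. Kaplan-Meier with that patient censored assumes the same future risk as in patients still alive, so its complement estimates what would happen if nobody died. That is not the rate of complications in the treated population. Deaths will accumulate over five years in this cohort; mortality is the primary endpoint.

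The progression-free survival row leaves it open for Graphs 4-8 whether death is itself an event. If it is, those curves show event-free survival and not the rate of the named complication. It cannot be so for Graph 9, which would then duplicate the all-cause curve of Graph 1. Neither reading gives the rate that the endpoint names.

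These are the safety and durability figures of a registry run for the reimbursement authority. Type 9 sets the crude percentage beside the Kaplan-Meier figure. The crude percentage is too low when patients are lost, and 1-KM is too high when deaths are censored, so the true incidence can lie between two printed numbers.

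**Working it through.** **Inputs.** From the documents: n = 160, follow-up of 5 years (1826 days), Kaplan-Meier, censoring at last observation. Assumed, because the documents give no expected values: true 5-year incidence I of 5%, 10% or 20%; share dying event-free by 5 years D of 15%, 20% or 35%. The plan has no figure of its own to reproduce here.

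**Direction.** With cumulative cause-specific hazards H_e (event) and H_d (death), the true incidence is ∫h_e·exp(−H_e−H_d)dt. Censoring deaths gives 1-KM = ∫h_e·exp(−H_e)dt, which can never be smaller.

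**Constant hazards, complete follow-up.** 1-KM = 1−(1−I−D)^(I/(I+D)). Examples:
- I = 0.20, D = 0.35: 1−0.45^0.3636 = 0.252
- I = 0.10, D = 0.20: 1−0.70^0.3333 = 0.112
- I = 0.05, D = 0.20: 1−0.75^0.2 = 0.056

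**Early events.** Two periods (days 0-30, then to 5 years) with constant hazards in each; 80% of events and 20% of event-free deaths fall in the first. For I = D = 0.20, period 1 has 0.16 events and 0.04 deaths, giving a factor 0.80^0.8 = 0.8365. Period 2 has 0.04 events and 0.16 deaths among the remaining 0.80, giving 0.75^0.2 = 0.9441. So 1-KM = 1−0.8365×0.9441 = 0.210.

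**Precision.** Half-width = 1.96·√(I(1−I)/160).

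| True I | Excess of 1-KM, constant hazards (D = 15 / 20 / 35%) | Excess, early events | 95% half-width |
|---|---|---|---|
| 20% | 1.8 / 2.5 / 5.2 points | 0.7 / 1.0 / 2.0 | 6.2 |
| 10% | 0.9 / 1.2 / 2.4 | 0.3 / 0.5 / 0.9 | 4.6 |
| 5% | 0.4 / 0.6 / 1.2 | 0.2 / 0.2 / 0.4 | 3.4 |

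**Late events.** This check assumes all-cause mortality instead of D. With 40% mortality and an event hazard rising linearly in time, a true 20% becomes 27.5%, an excess of 7.5 points that passes the 6.2-point half-width. A true 5% becomes 6.9%, an excess of 1.9 against 3.4. In relative terms the overstatement hardly depends on how frequent the event is (constant hazards, 40% mortality: ×1.27 at 3%, ×1.25 at 30%). Timing and mortality drive it.

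**Disease-related death.** Only unrelated deaths compete. If half of all deaths M are disease-related, 1-KM = 1−(1−M)^0.5 against M/2. For M = 15%, 20%, 35% this is 7.8%, 10.6%, 19.4% against 7.5%, 10.0%, 17.5%. SAP 2.5 counts every death within 30 days of the procedure as disease-related. If 60% of the disease-related deaths fall there, with no competing death in that period, 1-KM is 7.6%, 10.2%, 18.3%.

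**Loss to follow-up, I = D = 0.20.** The total cumulative hazard is −ln(0.60) = 0.5108, so event and death each have 0.2554. A loss hazard equivalent to 10% adds −ln(0.90) = 0.1054. The crude share is 0.2554/0.6162 × (1−e^−0.6162) = 19.1%. For 20% loss it is 0.2554/0.7340 × (1−e^−0.7340) = 18.1%. 1-KM stays at 22.5% in both cases. In simulation, Aalen-Johansen gives 20.1% and 20.0%, against a true 20%.

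**Simulation at the study size.** In 2,000 cohorts of 160 with 40% mortality, constant hazards and a true 20%, 1-KM averaged 25.2% with censoring at death and 26.3% with censoring at the last scheduled visit before death. Aalen-Johansen averaged 20.0%.

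**The case against.** The strongest reply is that the plan does not rest on these curves. Each endpoint also has a categorical rate over cumulative windows. With complete follow-up and deaths kept in the denominator, that proportion equals the Aalen-Johansen estimate. The censoring sentences sit under missing-data headings, and a dated death is not plainly missing data, so the documents leave the point open rather than prescribe the error. The progression-free row may be template text. The sizes are all assumed, mostly below the half-width, and no threshold or comparator depends on them. Protocol 5.4.2 also sets out steps that limit loss to follow-up.

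Much of this stands, and it limits the grade. The point is partly one of silence, the effect is modest for rare or peri-operative events, and no hypothesis test turns on it. It does not rescue the curves, because neither handling of death yields the named rate. Nor are the categorical rates a clear safeguard. SAP 2.1.1 divides by non-missing observations, SAP 2.1.3 treats a patient who interrupts the study as missing from the last follow-up, and neither says whether death counts as interruption. The layout that divides by all patients (Type 8) serves the adverse event table, whereas Tables 54-59 use Type 4, which has a row for missing values. If event-free deaths did leave that denominator, the rates would be worse than 1-KM: with 20% events and 35% event-free deaths, 0.20/0.65 = 30.8%.

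**Conclusion.** The concern holds and should be fixed. As the visible plan is written, the Kaplan-Meier complement for the six endpoints equals or exceeds the true 5-year incidence, and a larger sample would not remove the excess. Under the assumed inputs, the excess ranges from 0.2 points (rare, early events, 15% event-free deaths) to 5.2 points (20% incidence, constant hazards, 35% event-free deaths). It passes the confidence half-width only for frequent events under heavy mortality, for example late-rising re-interventions at 40% mortality. For disease-related death it is 0.1 to 1.9 points.

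The sizes rest on assumed mortality, incidence and timing; the direction rests only on deaths being censored. Confidence is medium because that censoring is a reading of a general rule and some text is not shown. All-cause mortality (Graphs 1-3) is unaffected.

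**What to change.** In SAP 2.4.3.2 and for Graphs 4-9:
- Replace Kaplan-Meier by the Aalen-Johansen cumulative incidence, with 95% confidence intervals at days 30, 365, 731, 1096, 1461 and 1826, the time-points of SAP 2.5.
- Define the competing event: death from any cause for the five non-fatal endpoints, and death not related to the disease for disease-related mortality.
- Give these endpoints their own table layout, without the survival-rate and progression-free survival rows. Keep Kaplan-Meier and Type 9 for all-cause mortality.
- State that patients who died event-free stay in the denominator of Tables 54-59, or take those rates from the same cumulative incidence function.

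The cost is SAP wording, one extra table layout, and re-programming of six graphs with their summary tables. No new data are needed, because deaths and their relation to the disease are already collected.
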